Therefore, two groups were formed: an intervention group of 30 patients who will receive the early Occupational Therapy program in addition to the rehabilitation that they would receive independently of this study, and a control group of 30 patients who will receive the conventional rehabilitation.

Eligible patients were assigned to EOTIPS or the control group according to a pre-established computer randomized designation in blocks of six.

Inclusion and exclusion criteria

All patients must have diagnostic confirmation of stroke with single or multiple vascular lesions that had occurred in the same time period, demonstrated by neuroimaging tests (CT or MRI), be over 18 years of age, go home on discharge and live within a maximum of 30 minutes away from the hospital center, with >2 or <26 points on the National Institute of Health scale (NIHSS), 30–100 points on the Barthel Index (BI) on the second day after the stroke (with BI 100, the patient

can be included if the Montreal Cognitive Assessment is <26) and having been referred to the rehabilitation service as an outpatient. Inclusion in the study occurs prior to hospital discharge, within a two- week interval after the stroke.

Exclusion criteria are: NIHSS > 26, BI < 30, and life expectancy < 1 year. Also excluded are people with a previous stroke, dementia or other types of diseases that cause dementia and other neurological, psychiatric or medical diseases (for example, severe epilepsy, traumatic brain injury, schizophrenia, COPD, severe or unstable heart disease, sleep apnea) concomitants that could alter cognitive function, presence of moderate or severe aphasia, people who do not understand Spanish or English, as well as patients who have been referred to the Physical Medicine and Rehabilitation Unit as inpatients to receive intensive rehabilitation or who are discharged to a care home.

The variables will take into account: age, sex, educational level, marital status, nationality, mother tongue, employment, vascular territory and lesion volume.

List of results and evaluations

Patient evaluations	
Quality of life	- SAQOL-39
Level of functional independence	- BI - mRS - SIS-16
Perceptual-cognitive skills	- MoCA
Sensory-motor skills	Fugl MeyerBergTime up & go
Communication skills	- CAL
Anxiety and/or depression levels	- Berg - Hamilton

Assessments to be used in the study (all translated into Spanish)

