- Stroke and Aphasia Quality of Life Scale 39, SAQOL-39 (Lata-Caneda, Piñeiro- Temprano, García-Fraga, García- Armesto, Barrueco-Egido, Meijide-Failde, 2009). SAQOL-39 was derived from the Stroke-Specific Quality of Life Scale and four additional items specifically targeting patients with aphasia, covering four domains: physical, psychosocial, communication, and energy.
- Montreal Cognitive Assessment, MoCA (Lozano Gallego, Hernández Ferrándiz, Turró Garriga, Pericot Nierga, López- Pousa, Vilalta Franch, 2009). MoCA has been proposed as a screening tool that promises good sensitivity to deficits resulting from stroke and vascular cognitive impairment. MoCA includes sections on visuospatial/executive functions, naming, attention, language, abstraction,

memory, and orientation. It is scored out of 30 (extra point for <13 years of education) and the recommended "normal" limit is ≥26.

- *Modified Rankin Scale*, *mRS* (Van Swieten, Kodustaal, Visser, Schouten, Van Gijn, 1988). The mRS is used to describe disability in general. The scale ranges from 0 to 6, from perfect health with no symptoms to death.
- Fugl-Meyer sensory motor assessment, FMA (Ferrer González, Zarco Periñán, Ruiz de Vargas, Docobo Durantez, 2015). It evaluates the upper extremity (maximum score of 66 which corresponds to normal motor function) and lower extremity (maximum score of 34). Tenderness, passive range of motion, and pain during passive joint movements are also evaluated.
- Timed up and go, TUG (Hafsteinsdóttiret al, 2014). TUG assesses basic mobility, timing the time required for a person to stand up from a standardized chair, walk a distance of three meters, turn, return to the chair, and sit down again. A shorter time indicates better performance. It has been shown to be reliable and valid in this group of patients.
- Berg Balance Scale, BBS (Kudlac, Sabol, Kaiser, Kane, Phillips, 2019). BBS assesses functional balance. Performance on this test is scored from 0 (unable to perform) to 4 (normal performance) on 14 different tasks, including the ability to sit, stand, reach, bend, turn, and step. The maximum score on the BBS is 56. A higher score indicates better balance skills.

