- Barthel Index, BI (Baztán, Pérez del Molino, Alarcón, San Cristobal, Izquierdo, Manzarbeitia, 1993). The Barthel Index measures the extent to which someone can function independently during basic activities of daily living (ADLs), i.e., feeding, bathing, grooming, dressing, bowel control, bladder control, grooming, chair transfers, ambulation and climbing stairs. Each performance element is rated on this scale with a given number of points assigned to each level. In this study, the modified version with 0–100 is used, where a lower score indicates dependence.
- Stroke Impact Scale 16, SIS-16 (Duncan, Lai, Bode, Perera, DeRosa, 2003). The usefulness of this scale is similar to that of the Barthel Index, although it is more sensitive than the latter for discriminating between patients with mild disabilities. It is designed especially for patients who have suffered a stroke, but it is also applicable to dementia. It is a reduced version of the Stroke Impact Scale version 3.0. The information can be obtained from the patient himself, or from the main caregiver (15) (16).
- Communicative Activity Log, CAL (Pulvermüller & Berthier, 2008). Scale that allows obtaining information on the communication capacity in the activities of daily life referring to comprehensive and expressive aspects of language. It is composed of 36 items (Likert-type scale, 0-6) that evaluate both the quality (items 1-18) and the quantity of patient communication (items 19-36). Performance is obtained through the sum of the scores on each item.

- Beck Depression Inventory, BDI-2 (Steer, Brown, 1996). It is a self-administered questionnaire that consists of 21 multiple-choice questions. It is one of the most commonly used instruments to measure the severity of depression.
- Hamilton Anxiety Scale (Lobo et al, 2002). This scale evaluates the severity of anxiety globally in patients who meet criteria for anxiety or depression. In addition, this instrument is useful to monitor the response to treatment. It is composed of 14 items, 13 referring to anxious signs and symptoms and the last one assessing the patient's behavior during the interview.

The evaluations were carried out in both groups (control and intervention group) before discharge (after completion of the informed consent) and three months after the neurological event.

Timeline and data collection

Hospital discharge planning

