The following analysis model was followed: to study the differences that may exist between one group and another, before and after the intervention, a repeated measures ANOVA was carried out; to check how some variables influence others, a multivariate analysis was carried out and, finally, to know the mean and normal distribution of the variables, descriptive statistics were performed. An intragroup analysis was included by performing paired T-test studies along with Wilcolxon for non-parametric measurements. The program used for data analysis was JAMOVI (version 2.3.26).

Difficulties and limitations of the study

Regarding the limitations of this study, it is worth highlighting the biases possibly derived from the adherence to treatment of the users and their caregivers, as well as the behavior and involvement of the family member in the process that will likely induce differences in the results. It is worth highlighting the importance of the word of the patient and the caregiver due to the telephone process of the intervention, since it can lead to differences in the instructions provided by the occupational therapist and, therefore, in the treatment and final result.

Furthermore, an important limitation is the heterogeneity of the sample, since we are generally talking about patients who have had a stroke of any location, extent and volume. The random distribution of patients may result in the two groups having significant differences in the severity of their injuries or their potential for recovery. Also due to the heterogeneity of each patient's rehabilitation process, it is understood that, of the total sample size, certain patients will subsequently receive a greater number of conventional rehabilitation sessions than others, and some patients will probably not even receive any sessions. This is why it seems

interesting to subsequently study the care received by each user three months after discharge, as well as their level of functionality and quality of life.

Ethical considerations

During data collection, the anonymity of users was guaranteed. Participants will be informed of the intervention and will be asked to sign an informed consent, with participation being voluntary and allowing the user to abandon whenever they wish.

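### TUG: the only between-arm analysis specified is a repeated measures ANOVA with no baseline covariate or transformation stated, which costs power, and nothing says how patients without a time are counted

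*Combined protocol and SAP*

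**What the plan says.** The Results analysis plan assigns one method to differences between the arms: "to study the differences that may exist between one group and another, before and after the intervention, a repeated measures ANOVA was carried out". It names no model term, baseline covariate or transformation.

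Three other statements in that section bear on the point:

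- Distributions are looked at descriptively: "to know the mean and normal distribution of the variables, descriptive statistics were performed". No consequence for the between-arm analysis is tied to this.
- A non-parametric option appears only for within-arm change: "An intragroup analysis was included by performing paired T-test studies along with Wilcolxon for non-parametric measurements".
- A multivariate analysis is mentioned, for how variables influence one another. It lists no outcome and no covariates.

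TUG is listed under sensory-motor skills, which the Specific Objectives make a secondary result. It is defined purely as a completed time ("timing the time required for a person to stand up from a standardized chair", walk three metres, return and sit), and "A shorter time indicates better performance". The Berg scale, by contrast, has a value for inability: each task is "scored from 0 (unable to perform) to 4 (normal performance) on 14 different tasks". Both scales are assessed "before discharge (after completion of the informed consent) and three months after the neurological event". Eligibility requires a score of 30 to 100 "points on the Barthel Index (BI) on the second day after the stroke".

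**The concern.** Completion times are often right-skewed, and the plan's response to a non-normal outcome reaches only the within-arm tests, which do not estimate the effect of the intervention. The between-arm test stays on raw seconds and uses baseline only by subtraction, although baseline TUG is measured in everyone able to do it. A real TUG benefit could be missed with 30 patients per arm.

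There is also a coverage question. TUG has no score for a patient who cannot do it, and the documents state no rule for such a patient and no missing-data method. A two-visit repeated measures ANOVA uses only patients with a value at both visits. A patient who goes from unable to able would then probably not count, and a reader would not know how many patients the TUG result describes.

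**Working it through.** **The plan's own figure.** The sample size rests on SAQOL-39, not TUG: SD 0.75, difference 0.54, 5% significance, 80% power. Taking the test as two-sided, n per arm = 2 × (1.96 + 0.8416)² × 0.75² / 0.54² = 30.3, so the stated 30 reproduces to within rounding. No size or power is stated for TUG, so everything below is on assumed values.

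**What the planned test is.** With two visits, the group-by-time F test equals a two-sample t-test on change (3 months minus baseline).

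**Roughly symmetric times.** With equal variance σ² at both visits and correlation r:

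- variance of change = 2(1 − r)σ²
- residual variance in ANCOVA = (1 − r²)σ²
- ratio = 2/(1 + r), which is 1.25 at r = 0.6 and 1.11 at r = 0.8

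With 30 per arm, an effect of 0.6σ and a two-sided 5% test, the noncentrality is 0.6 × √15 / √(variance/σ²):

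| r | Change: noncentrality, power | ANCOVA: noncentrality, power |
|---|---|---|
| 0.4 | 2.12, 55% | 2.54, 70% |
| 0.6 | 2.60, 72% | 2.90, 81% |
| 0.8 | 3.67, 95% | 3.87, 97% |

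Simulation with normal times (mean 20 s, SD 5-6 s) agrees: at r = 0.6, about 71-72% for the planned test and 80-82% for ANCOVA in seconds; at r = 0.8, about 95% and 96%. ANCOVA on log times does worse than ANCOVA in seconds here: 76-78% at r = 0.6. At r = 0.8 it has no lead over the planned test (94-95% for both).

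**Right-skewed times.** Log-normal times, log SD 0.4 to 0.8, r = 0.6, effect 0.6 SD of log time, 30 per arm, everyone timed:

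| Analysis | Power |
|---|---|
| Planned test, raw change | 33-55% |
| ANCOVA in seconds | 63-77% |
| Change in log time, no covariate | 72% |
| ANCOVA on log times | 81% |
| ANCOVA on ranks | 77% |

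Type I error is about 4-5% for the planned test and the ANCOVAs. The loss therefore comes from skew and from the missing baseline covariate, and not from the absence of a rank test as such.

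If the group main effect were meant instead of group-by-time, power would be lower: 7-22% across log SD 0.3-1.0 and r 0.5-0.85, with the effect sized to give ANCOVA on log times about 80%. On the same settings the group-by-time test has 26-52%.

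**Patients without a time.** The rates here are assumptions; the documents give none.

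- *Who is kept.* With 10% or 30% unable, the two-visit ANOVA keeps about 53 or 39 of 60 patients. About 5 or 12 of those left out go from unable to able.
- *Size of the estimate.* With log SD 0.5, r = 0.7 and a benefit of 0.25 on the log scale, suppose times above 60, 40, 35 or 30 s cannot be obtained. The mean difference then moves from about −6.3 s in all patients to −5.5, −4.3, −3.8 or −3.2 s in those timed at both visits.
- *If treatment affects who can be timed.* Suppose the intervention only enables slow patients (10-30%) to perform and changes nothing else. The comparison of timed patients then makes the intervention look 1.3-2.4 s worse, with 7-9% rejection.

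**The case against.** **The multivariate analysis might adjust for baseline.** It could include arm and baseline TUG. It is given another purpose and lists neither outcome nor covariates, so the supportable statement is that the ANOVA is the only between-arm analysis specified, and that no covariate or transformation is stated. This limit on the wording stands.

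**Change-score analysis is an accepted method.** It is, and it does use baseline, by subtraction. A reader might infer that the planned test is invalid for skewed times; the type I error figures do not support that. They cover only the case of no effect, however. They do not make the estimate in timed patients describe all randomised patients if treatment affects who can be timed.

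**The skew is assumed.** True. A reader might infer that log times are always the better choice. They are not: with symmetric times ANCOVA in seconds does better, and at high correlation the log analysis gains nothing over the plan. Log times need a condition.

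**Exclusion of patients unable to do TUG is inferred.** Also true, and this objection largely stands. A reader might infer that such patients existed and were dropped. The Barthel floor of 30 applies on day 2, TUG was done later, before discharge, and these patients were going home as outpatients. The documents say neither that anyone was unable nor how such a patient was coded. This supports reporting counts; it does not show an error.

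**TUG is one of several secondary scales and the project is complete.** Both are so, and they set the priority.

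**Conclusion.** The point holds as a minor one. The planned TUG comparison has type I error near 5% under no effect but is less efficient than a baseline-adjusted analysis of the same data. The power loss is about 9 points at r = 0.6 with symmetric times and nearly vanishes at r = 0.8. With log-normal times at r = 0.6 it is roughly 20-30 points against ANCOVA in seconds and 26-48 points against ANCOVA on log times (81 − 55 and 81 − 33). These sizes rest on the assumed effect, correlation and distribution; only the 30 per arm and the two visits come from the documents. The coverage part is a gap in reporting, with size unknown.

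**What to change.** Keep the planned ANOVA and name the term that tests the intervention. Add, disclosed as post hoc:

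1. An ANCOVA of 3-month TUG on baseline TUG and arm, with a 95% CI. Use seconds by default. Use log times, reported as a ratio of times, only if the pooled distribution, examined without regard to arm, is right-skewed.
2. The number of patients with no TUG time, by arm and visit.
3. If inability was recorded and is not rare, a sensitivity analysis by worst-rank ANCOVA (unable ranked worst at each visit). Choose it for whom it covers and not for power: if patients unable at baseline gain nothing, it has 70% and 49-50% power with 10% and 30% unable, against 72% and 53% for ANCOVA on log times.

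Rest efficacy statements on the between-arm contrast and give within-arm changes as description.

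The cost is small: one extra model on data already collected, labelled post hoc because the Time planning section reports the project complete. On the log or rank scale the result is no longer in seconds. ANCOVA still leaves out untimed patients, and the worst-rank analysis is possible only if inability was recorded, which the documents do not say.

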We designed a four-week early OT intervention program for patients who have suffered a stroke with the aim of improving quality of life and facilitating their return home by providing them and their caregiver with knowledge about specific care and neurorehabilitation.

Specific Objectives

Primary outcome: Quality of life. Secondary results: Functional independence and support needs in activities of daily living, sensory-motor skills, perceptual-cognitive skills, communication skills, anxiety and depression levels.

Methods

Type and general design of the study

This is a prospective, randomized, controlled clinical trial. The population to be represented is that of patients who are discharged from the neurology service of the Virgen de la Victoria University Hospital (Malaga) and who, after medical discharge, are referred to the rehabilitation service of the Maritime Hospital of Torremolinos as outpatients by decision of the neurology and rehabilitation departments, but will not be inpatients in the Physical Medicine and Rehabilitation Unit for intensive rehabilitation.

Users who are referred to rehabilitation by obtaining a place as an inpatient, receive occupational therapy and physiotherapy daily for a period of maximum three months. However, patients who are referred to the rehabilitation service as an outpatient are taken home directly after discharge and are subsequently recalled for rehabilitation. The period that elapses from when they are discharged until they are called to begin their rehabilitation varies depending on the workload of the service, and can even be three months after discharge. Referral to external or intensive rehabilitation is made based on the rehabilitation potential, which takes into account certain criteria such as age, clinical situation and vascular injury existing at the time of discharge, social support, motivation and observed recovery. during admission. Patients assigned to the study program are included in an early occupational therapy intervention program and are compared with a control group that will receive usual care and rehabilitation.

Sample selection and size

The sample size "n" was calculated based on the main variable SAQOL-39 with the sample size determination formula for two independent groups, assuming a mean of 2.50, standard deviation of 0.75, significance level of 5%, a power of 80% and a critical difference of 0.54, obtaining a sample of 30 participants per group.

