The rehabilitation and neurology departments were responsible for referring patients to the occupational therapist and including them in the study. Before starting rehabilitation, the occupational therapist and her family explored the patient's needs and desires and decide individual goals for the intervention period.

Occupational Therapy intervention during the discharge process. The intervention has a person-centered approach that is based on who the user is: their context, their history, their family members, their individual strengths and weaknesses. Individualized objectives will be established, taking into account the patient's potential and limitations. Examples of goals could be: being able to wash independently, hanging clothes or riding the bus, or how to manage bills. OT intervention may involve training in different activities or thinking about different ways to adapt to difficult situations to achieve a goal. For example, for some patients the intervention may consist of carrying out

ADLs in which they have a limitation with the support of the occupational therapist with the aim of enhancing their sense of security during its performance. Data will be collected through note taking and analyzed with qualitative content analysis.

The designed OT intervention includes:

- Prior to discharge: Initial evaluation and a hospital session.
- Post-discharge: A two-hour home visit, telephone follow-up, a one-hour visit one month after discharge and final evaluation three months later.

This early OT intervention will be carried out independently of the usual care of the rehabilitation service of the Torremolinos Maritime Hospital.

Time planning

The project will begin in January 2021 and was estimated to last one year and three months (estimated completion in March 2022). Finally, the project was completed on November 2022.

Day 1: Hospital (1 hour)					
Initial interview and evaluation.					
Day 2: Hospital (1 hour)					
Information about stroke. Postural care.					
Day 3: Home (2 hours)					
Environment assessment, equipment and					
recommendations and establishment of					
individualized objectives.					
Day 4 - day 29: PHONE FOLLOW-UP.					
Implementation of the rehabilitation by the patient					
and caregiver (individual objectives).					
Day 30: Home (1 hours).					
Final assessment of individualized objectives at					
home.					
After 3 months: Home (1 hour)					
Final evaluation.					

Results analysis plan

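### The between-arm test is a two-time-point repeated measures ANOVA with no named treatment term; ANCOVA on the baseline SAQOL-39 already collected is at least as precise, apart from a small covariate cost, and handles chance baseline differences better

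*Combined protocol and SAP*

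**What the plan says.** - **Between-arm analysis (Results analysis plan).** To compare the groups, "before and after the intervention, a repeated measures ANOVA was carried out". No model term, covariate, effect estimate or confidence interval is specified.
- **Other modelling (same section).** "to check how some variables influence others, a multivariate analysis was carried out". No outcome, covariate list or treatment comparison is attached to this, so it cannot be read as baseline adjustment of the primary comparison. What remains is descriptive statistics and within-group paired tests.
- **Measurement times (end of the list of assessments).** Both groups are evaluated "before discharge (after completion of the informed consent) and three months after the neurological event". A baseline SAQOL-39 therefore exists in both arms. The day-30 visit reviews individual goals and is not a third SAQOL-39 time point.
- **Sample size (Sample selection and size).** It was "calculated based on the main variable SAQOL-39 with the sample size determination formula for two independent groups", with "standard deviation of 0.75, significance level of 5%, a power of 80% and a critical difference of 0.54", giving 30 per group.
- **Expected imbalance (Difficulties and limitations of the study).** The plan warns that random allocation "may result in the two groups having significant differences in the severity of their injuries".
- **Status (Time planning).** "Finally, the project was completed on November 2022".

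**The concern.** With two groups and two measurements, the group-by-time F test is the square of the t-test on change from baseline. A change score fixes the baseline slope at 1. If the true slope is below 1, as it must be when the two SDs are equal and r is below 1, the test over-corrects a chance baseline difference. ANCOVA estimates the slope from the data.

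With only 30 patients per arm, and a plan that itself expects the arms may differ, two things are at stake: a wider confidence interval than the data allow and, in a trial with a chance baseline difference, an estimate shifted in either direction.

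The unnamed term is a lesser part of the point. The wording suggests the interaction, but a repeated measures ANOVA also gives a group main effect, and that averages in the pre-treatment score.

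**Working it through.** **Inputs from the plan.** Difference 0.54, SD 0.75, alpha 5% (two-sided assumed), power 80%, 30 per arm.

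**Assumptions.** The plan does not give r, so 0.3, 0.5 and 0.7 are shown. It does not say what the 0.75 describes; it is taken as the SD of a single 3-month score (SD1). The baseline SD (SD0) is first set equal to SD1, then varied.

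**1. The plan's own figure.** n = 2 × [0.75 × (1.960 + 0.842) / 0.54]² = 30.28 per arm. This matches the stated 30 (31 if rounded up). Power at 30 per arm is 79.6% by the normal approximation and 78.3% by noncentral t with 58 df.

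**2. Variances per patient.**
- Change score (interaction): SD0² + SD1² − 2r·SD0·SD1, with 58 df.
- ANCOVA: SD1²(1 − r²), with 57 df, multiplied by 1 + 1/56 for estimating the slope.
- Before that multiplier, the first minus the second is (SD0 − r·SD1)², which is never negative.
- With equal SDs the ratio is 2(1 − r)/(1 − r²) = 2/(1 + r).

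**3. Equal SDs.** SE = √(variance × 2/30); power by noncentral t.

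| r | Variance ratio | Power, interaction | Power, ANCOVA | Mean 95% CI width, interaction | Mean 95% CI width, ANCOVA |
|---|---|---|---|---|---|
| 0.3 | 1.54 | 64.0% | 81.3% | 0.91 | 0.74 |
| 0.5 | 1.33 | 78.3% | 88.0% | 0.77 | 0.67 |
| 0.7 | 1.18 | 94.3% | 96.7% | 0.60 | 0.56 |

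Simulation with 20,000 trials per r agrees to within about one point. The interaction reaches 80% power just above r = 0.52, and ANCOVA just above r = 0.24.

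**4. Unequal SDs.** SD1 stays at 0.75, so ANCOVA stays at 81%, 88% and 97%.

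| Baseline SD | Interaction, r = 0.3 | r = 0.5 | r = 0.7 |
|---|---|---|---|
| 0.94 | 53% | 67% | 86% |
| 0.56 | 74% | 86% | 97% |
| 0.375 | 80% | 89% | 96% |

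The gain vanishes where SD0 is close to r·SD1: at SD0 = 0.375 with r = 0.5, and at SD0 = 0.56 with r = 0.7 (interaction 96.9%, ANCOVA 96.7%).

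**5. If 0.75 is instead the SD of change (equal SDs).** The interaction has 78% power at every r. ANCOVA has 92%, 88% and 84% at r = 0.3, 0.5 and 0.7.

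**6. Chance imbalance.**
- The SE of the baseline difference is 0.75 × √(2/30) = 0.194 with equal SDs. A difference of at least 0.20 in either direction then occurs in about 30% of trials this size. It occurs in 17% at SD0 = 0.56 and 4% at SD0 = 0.375.
- A difference of exactly 0.20 shifts the change-score estimate by (1 − r·SD1/SD0) × 0.20. With equal SDs that is 0.14, 0.10 and 0.06 at r = 0.3, 0.5 and 0.7.
- Among simulated null trials with at least that imbalance (equal SDs), the interaction's type I error is about 11%, 9% and 7%, against about 5% for ANCOVA. Over all trials both hold 5%.

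**7. The group main effect.** Averaging baseline and 3-month scores halves the treatment effect. Rescaled to the 3-month effect, the variance is 2(1 + r)·SD². With equal SDs, power would be about 40%, 35% and 32% at r = 0.3, 0.5 and 0.7.

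**The case against.** The strongest reply is that nothing here is an error. The interaction test is unbiased over randomisation and holds its 5% level. At r = 0.5 with equal SDs it has 78.3% power, the same as the two-sample comparison on which the trial was sized. The size of any gain depends on r and the baseline SD, neither of which the plan gives, and the conditional type I figures are for equal SDs: at baseline SD 0.56 with r = 0.7 the excess disappears. The wording already suggests group-by-time. The plan's worry is injury severity, for which baseline quality of life is only a proxy. With the project complete, a new analysis cannot be prespecified.

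Most of this stands, and it limits the weight of the point. It does not remove it. The direction of the precision comparison does not depend on r or the SDs. In the grid above, the most ANCOVA loses is about 0.6 points of power (baseline SD 0.375, r = 0.5), while with equal SDs it gains about 17 points at r = 0.3 and 10 at r = 0.5. The main-effect reading is one that no passage adopts; a single sentence would rule it out.

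**Conclusion.** The concern holds, as a matter of efficiency and conditional precision and not of validity. The stated between-arm test makes no use of the baseline SAQOL-39 as a covariate, although it is collected in both arms. With equal SDs and r from 0.3 to 0.7, the change-score variance is 1.54 to 1.18 times the ANCOVA variance, and a chance baseline difference of 0.20 moves the change-score estimate by 0.14 to 0.06. The size rests on the assumed r, on a baseline SD the plan does not give, and on reading 0.75 as the SD of a single score; the gain can be nil when the baseline SD is smaller than the 3-month SD. ANCOVA's handling of imbalance assumes a linear baseline slope. The trial is not shown to miss its stated 80% power. The change should be made because it costs almost nothing.

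**What to change.** 1. Analyse 3-month SAQOL-39 by ANCOVA with randomised group as factor and baseline SAQOL-39 as covariate, keeping patients in the arm assigned. Report the adjusted mean difference with its 95% confidence interval.
2. Report the repeated measures ANOVA beside it, and state that the group-by-time interaction is its treatment test.
3. Because the project is reported complete, label the ANCOVA as specified after completion.
4. Use the same baseline-adjusted model for the other continuous scales, but not for the ordinal mRS.
5. Consider adding screening NIHSS as a severity covariate. It would come from the eligibility record, since it is in neither the evaluation list nor the listed variables. It meets the plan's severity concern only in part, and no power gain is claimed for it.

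**Cost.** No new data; one or two degrees of freedom, the small variance inflation shown above, and the linear-slope assumption. If NIHSS explained nothing, the factor would be 1 + 2/55 with 56 df. Power with equal SDs would then be about 81%, 87% and 96.5% at r = 0.3, 0.5 and 0.7, less than one point below the single-covariate model.
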